## DOCUMENT HISTORY

Document	Date of Issue	Summary of Change
Revised Protocol 05	18-Dec-2019	

Removed restriction of Part 1 enrollment from US sites only

Allowed less frequent imaging for long-term responders

Clarified laboratory collection for TSH and albumin

Updated interim analyses

Added myocarditis to Management Algorithms

Revised Protocol 04	03-May-2019	

Updated objectives, endpoints, and analyses for tissue and blood TMB

Updated and reorganized biomarker collection and removed receptor occupancy

Allowed skipped dosing on D15 and D29 only

Required brain imaging at screening and when clinically indicated

Updated schemas, interim analyses, dosing details, and appendices

Removed communication with medical monitor for insufficient tissue

Revised Protocol 03	02-Mar-2018	Incorporates Amendment 05
Amendment 05	02-Mar-2018	

Added Part 2 of protocol to include new participants for additional biomarker collection, objectives, endpoints, Procedural Outlines, [REDACTED]

Updated to allow for archival tissue in Part 1 for PD-L1 screening assessment/group assignment only

Added 2 year maximum duration of treatment

Removed fine needle aspirate tissue collection

Updated exclusion criteria, prohibited treatments, and discontinuation criteria to align with current nivolumab program standards

Added EudraCT number

Added Appendix 8 Country Specific Amendment for HIV testing

Revised Protocol 02	29-Mar-2017	Incorporates Amendment 04
Amendment 04	29-Mar-2017	
Protocol amendment is being implemented to include a co-primary objective to evaluate tumor mutational burden (TMB) as a candidate biomarker of clinical efficacy of nivolumab and ipilimumab combination therapy. [REDACTED]
 
[REDACTED] Dosing for nivolumab was changed to a flat dose of 240mg every 2 weeks. Women of Childbearing Potential definitions and methods of contraception were updated to align with program level guidance
 

1) Synopsis Updated:

a) Objectives and Endpoints: Updated to include a co-primary objective/endpoint to evaluate tumor mutational burden as a candidate

Document	Date of Issue	Summary of Change
		
biomarker of clinical efficacy of nivolumab and ipilimumab combination therapy.
 
b) Overall Design, Study Schematic, and Study Treatment: Updated to reflect nivolumab flat dose of 240mg every 2 weeks. Treatment and follow-up period were added to Schematic.
 
2) Table 2-1, Screening Procedural Outline:
 
 
a) Timing of pregnancy test for WOCBP clarified.
 
b) Body Surface Area removed from Physical Measurements.
 
c) Laboratory Tests clarified. Phosphorus required at screening and TSH + Free T3/T4 required within 72 hours of C1D1.
 
d) Paired Fine Needle Aspiration (FNA) added.
 
 
3) Table 2-2, On Treatment Procedural Outline:
 
 
a) Physical Exam: Removed reference to nivolumab weight based dosing and added reference to nivolumab flat dosing.
 
b) Laboratory Tests clarified. Phosphorus added for consistency with Section 9.4.1. TSH + Free T3/T4 required within 72 hours of C1D1 and TSH with reflexive Free T3/T4 on Day 1 of each Cycle thereafter (every 6 weeks).
 
c) Paired FNA to be collected from biopsies at Cycle 1 Day 29 (Week 5) and upon documented progression.
 
 

 
g) Reference to RO added for Whole Blood Collection.
 
4) Table 2-3, Follow-Up and Survival Procedural Outline:
 
 
a) Laboratory Tests clarified. Phosphorus and Albumin added for consistency with Section 9.4.1.
 
b) Reference to Biomarker assessments/PD Sampling removed.
 
 
5) Section 3.1, Study Rationale: Added rationale for inclusion of tumor mutational burden as a study objective.
 
6) Section 3.2.2, Rationale for combination of nivolumab and ipilimumab: Updated to reflect nivolumab flat dose of 240mg every 2 weeks.
 
7) Section 3.2.2.1, Rationale for Nivolumab Flat Dosing: Section added.
 
8) Section 3.2.5, Research Hypothesis: Added reference to TMB.
 
9) Table 4-1, Objectives and Endpoints: Updated to include a co-primary objective/enpoint to evaluate tumor mutational burden as a candidate biomarker of clinical efficacy of nivolumab and ipilimumab combination therapy.
 
10) Section 5.1, Overall Design: Updated to reflect nivolumab flat dosing.
 
11) Figure 5.1-1, Study Design Schematic: Updated to reflect nivolumab flat dose of 240mg every 2 weeks. Treatment and follow-up period were added to Schematic.
 
12) Section 5.5 , Justification for Dose: Updated to reflect nivolumab flat dose of 240mg every 2 weeks.


Document	Date of Issue	Summary of Change
		
13) Table 7.1-1, Selection and Timing of Dose: Updated to reflect nivolumab flat dose of 240mg every 2 weeks.
 
14) Section 7.1.1, Dosing Details: Updated to reflect nivolumab flat dose of 240mg every 2 weeks.
 
16) Table 9.4.1-1 Laboratory Assessment Panels
 
 
a) TSH and Free T3/Free T4 testing clarified.
 
b) Testing for Drugs of Abuse Removed.
 
 
17) Table 9.6-1, Biomarker Assessment Schedule:
 
 
a) Paired FNA collection added.
 
 
19) Section 9.6.11, Paired FNA Collection: Section added.
 
21) Section 10.1, Sample Size Determination: Updated to reflect tumor mutational burden as a co-primary objective.
 
22) Section 10.2, Populations for Analysis: Defined tumor mutational burden evaluable patients.
 
23) Section 10.3, Statistical and Computational Analyses: Updated to reflect the association between ORR and tumor mutational burden will be explored using logistic regression model among treated patients evaluable for tumor mutational burden.
 
24) Section 10.3.1, Efficacy Analyses: Updated to reflect the association between ORR and TMB will be explored using logistic regression model.
 
25) Appendix 4, Women of Childbearing Potential definitions and methods of contraception: Appendix was updated to align with program level guidance.

Revised Protocol 01	03-Nov-2016	Incorporates Amendment 02
Amendment 02	03-Nov-2016	
Protocol amendment is being implemented to include a blood collection for Receptor Occupancy Measurements and language to align with program level standards for dosing administration.
 
 
1) Section 2, Screening Procedural Outline: Tumor tissue samples from biopsies will be divided into FFPE and a fresh sample in preservative, not frozen.
 
2) Section 7.4.5.1, Criteria to Resume nivolumab Dosing: Removed repeated criteria.
 
3) Section 8.1.1, Nivolumab or Ipilimumab Dose Discontinuation: Criteria updated to reflect program standards.
 

Document	Date of Issue	Summary of Change
		

4) Section 8.1.3, Post Treatment Study Follow-Up: Updated to reflect program language.

5) Section 9.6, Biomarkers: Tumor tissue samples from biopsies will be divided into FFPE and a fresh sample in preservative, not frozen.

6) Table 9.6-1, Biomarker Assessment Schedule: Receptor Occupancy Whole Blood Collection Added.

7) Section 9.6.10, Receptor Occupancy Measurements: Section added.

8) Various typographical errors corrected.

Original Protocol	28-Sep-2016	Not Applicable

## OVERALL RATIONALE FOR REVISED PROTOCOL 05:

The CA209592 protocol was revised to allow addition enrollment at non-US sites for Part 1 and update the timing of the interim analyses. Additional updates provided internal consistency in the document.

SUMMARY OF KEY CHANGES FOR REVISED PROTOCOL 05		
Section Number & Title	Description of Change	Brief Rationale
Synopsis Study Schema Figure 5.1-1: Study Design Schematic Part 1 and Part 2	Removed restriction of Part 1 enrollment from US sites only Rationale:	Allows for additional enrollment for non-US sites for part 1.
Table 2-2: On Treatment Procedural Outline (CA209592) for Part 1 Table 2-3: On Treatment Procedural Outline (CA209592) for Part 2 Table 2-4: Follow-Up and Survival Procedural Outline CA209592 (All Treatment Groups Part 1 and Part 2)	Clarified laboratory collection for TSH and albumin	Updated document for internal consistency in document
Table 2-4: Follow-Up and Survival Procedural Outline CA209592 (All Treatment Groups Part 1 and Part 2) Section 9.1.1.1 Efficacy Assessments using CT scan or MRI Table 9.1.1.1-1: Imaging Assessment Schedule (Part 1 and Part 2)	After 3 years on study, tumor assessments for long-term survivors can be performed at a frequency per institutional guidelines or every 24 weeks based on NCCN surveillance guidelines.	Aligns imaging assessments with clinical practice for long-term responders.
Table 9.6-1: Biomarker Assessment Schedule for Part 1	Updated biomarker collection	Provides internal consistency in the document
Table 2-1 Screening Procedural Outline (CA209592) for Part 1 and Part 2 Table 2-2: On Treatment Procedural Outline (CA209592) for Part 1 Table 2-3: On Treatment Procedural Outline (CA209592) for Part 2 Section 9.1.1.1 Efficacy Assessments using CT scan or MRI	Updated clinical laboratory collection	Provides internal consistency in the document
Section 5.1 Overall Design Section 10.3.5 Interim Analyses	Updated language for Part 2 interim analysis sample size:	Updates document with original planned analysis with sample size (~150 pts).
Appendix	Added myocarditis to Management Algorithms	Aligns with program standards

## 1       SYNOPSIS

**Protocol Title:** An Exploratory Study of the Biologic Effects and Biomarkers of Nivolumab in combination with Ipilimumab in Subjects with Treatment-Naive Stage IV or recurrent Non-Small Cell Lung Cancer (NSCLC)

(CheckMate 592: CHECKpoint pathway and nivoluMAb clinical Trial Evaluation 592)

**Study Phase:**

Phase 2, exploratory

**Rationale:**

Immune checkpoint signaling through the programmed death 1 (PD-1) axis to its ligand (PD-L1) with or without CTLA-4 inhibition significantly dampens anti-tumor immune responses in different tumor types including NSCLC. Unfortunately, not all patients respond to immune checkpoint blockade, therefore there is a compelling need for a better understanding of factors that would predict response and progression.

Emerging science and evidence from multiple studies, including exploratory analyses from the phase 2 study CA209568 (nivolumab + ipilimumab) and phase 3 study CA209026 (nivolumab monotherapy), tumor mutational burden (TMB) was identified as an important potential biomarker (independent of PD-L1) to help identify patients most likely to benefit from immunotherapy.

CA209592 is a two-part, exploratory, phase 2 open-label study aiming to explore potential biomarkers of response, including tumor mutational burden, and their association with clinical benefit when nivolumab + ipilimumab combination is given as primary therapy for advanced or metastatic NSCLC, regardless of PD-L1 expression (Part 1). Part 2 of the study explores the association between TMB (blood and tissue) and clinical efficacy.

In Part 1, changes occurring in candidate biomarkers within the tumor or within the peripheral blood during treatment, or at the time of disease progression, may provide an understanding of the mechanism of action, and the biology of underlying response (efficacy/safety) and/or underlying acquired resistance, which may help inform future combination strategies.

Based on the Part 2 expansion cohort in this study, tumor TMB and blood TMB will be collected at baseline. The association of tissue and blood TMB analyses with clinical outcomes will be assessed independently.

**Study Population:**

Participants with Stage IV or recurrent NSCLC, with no prior systemic anticancer therapy given as primary therapy for advanced or metastatic disease.

## Part 1 Objectives and Endpoints:

Objectives	Endpoints
Primary	

• To evaluate baseline tumor mutational burden as a candidate biomarker of clinical efficacy of nivolumab and ipilimumab combination therapy.

• To investigate the potential association between candidate biomarkers in peripheral blood and tumor tissue at baseline and on-treatment with clinical efficacy measures.

	

• The clinical efficacy will be measured by the analysis endpoint of objective response rate (ORR). The association of ORR with candidate biomarkers in peripheral blood and tumor tissue at baseline and on-treatment will be assessed. Candidate biomarkers may include:

◦ Baseline tissue TMB and blood TMB

◦ Potential biomarkers/signatures (including PD-L1 expression) both at baseline and on treatment

◦ Immunomodulatory and pharmacodynamic activity

Secondary	

• To evaluate efficacy in patient subgroups defined by baseline discovery biomarkers.

	

• ORR, disease control rate (DCR)

• Duration of response (DOR) and time to response (TTR)

• Progression free survival (PFS)

• Overall survival (OS)

**Part 2 Objectives and Endpoints:**

Objectives	Endpoints
Primary 

To evaluate the association between baseline tissue TMB/blood TMB and clinical efficacy (ORR) for participants in Part 2

	

The clinical efficacy will be measured by the analysis endpoint of objective response rate (ORR). The association of ORR with baseline tissue TMB and blood TMB will be assessed.

Secondary 

To investigate bacterially-generated and human components enteric biomarkers and identify potential associations with clinical outcomes, including safety and efficacy, for subjects in Part 2.

	

ORR, PFS, OS

Incidence of AES, SAEs, and select AEs

**Overall Design:**

Protocol CA209592 is an open-label, exploratory trial evaluating nivolumab in combination with ipilimumab in participants  $\geq$  18 years old with histologically confirmed advanced or metastatic NSCLC, with no prior systemic anticancer therapy given as primary therapy for advanced disease.

In Part 1, participants will undergo screening evaluations to determine eligibility within 28 days prior to cohort assignment, and approximately 100 patients will be treated. Tumor sample for PD-L1 status assessment is required at screening for group assignment.

Upon determination of PD-L1 status (cut-off of 1%), 2 cohorts will be defined: PD-L1 positive and negative, and patients in each cohort (n= 50 ea.) will receive nivolumab + ipilimumab.

In Part 2, approximately 150 participants will be assigned to a single cohort and treated with nivolumab + ipilimumab regardless of their PD-L1 status.

All participants will be treated with the following:

[figure not shown]
- nivolumab 240mg IV every 2 weeks + ipilimumab 1 mg/kg IV every 6 weeks until disease progression, unacceptable toxicity, withdrawal of consent, the study ends, or maximum treatment duration of 2 years, whichever occurs first. Participants will be permitted to continue on nivolumab +/- ipilimumab beyond initial RECIST 1.1 defined progression, as long as they meet the criteria described in [Section 8.1.2](#).

### Number of Participants:

**Part 1:** Approximately 150 participants are expected to be enrolled to achieve approximately 100 treated participants in the trial.

**Part 2:** Approximately 200 participants are expected to be enrolled to achieve 150 treated participants. Sites in US and Europe may participate in Part 2.

### Study Schematic Part 1 and Part 2:

### Study treatment:

Study Drug for CA209592			
Medication	Dosage level(s)	Frequency of Administration	Route of Administration
nivolumab	240mg	Every 2 weeks	IV
ipilimumab	1 mg/kg	Every 6 weeks	IV

## 2 SCHEDULE OF ACTIVITIES

**Table 2-1: Screening Procedural Outline (CA209592) for Part 1 and Part 2**

Procedure	Screening Visit a	Notes
Eligibility Assessments		
Informed Consent	X	ICF signed during screening for protocol participation prior to any study specific procedures. Study allows for re-enrollment of a participant that has discontinued the study as a pre-treatment failure. If re-enrolled, the participant must be re-consented and assigned a new patient ID number from IWRS.
Inclusion/Exclusion Criteria	X	All inclusion/exclusion criteria should be assessed at screening and confirmed prior to dosing. Section 6 .
Medical History	X	
Body Imaging	X	Contrast enhanced CT of the chest, CT/MRI of the abdomen, pelvis, and all other known and/or suspected sites of disease, within 28 days prior to the first dose [REDACTED]
Brain Imaging	X	MRI of the brain without and with contrast is required for ALL participants during screening to rule out brain metastases. CT of the brain (without and with contrast) can be performed if MRI is contraindicated. See Section 9.1.1 and Appendix 6 for further details.
Prior Systemic Therapy	X	Any prior medications received to treat cancer.
ECOG Performance Status	X	ECOG Status of 0 or 1 required for treatment assignment. Appendix 5 .
Safety Assessments		
Physical Measurements	X	Includes height and weight
Full Physical Examination	X	Within 14 days prior to first dose.
Vital Signs	X	Including seated blood pressure, heart rate, and temperature.
Assessment of Signs and Symptoms	X	Within 14 days prior to first dose.

**Table 2-1: Screening Procedural Outline (CA209592) for Part 1 and Part 2**

Procedure	Screening Visit a	Notes
Concomitant Medication Collection	X	Within 14 days prior to first dose.
Laboratory Tests	X	
Section 9.4.1, Within 14 days prior to first dose.
 
CBC w/differential, Chemistry panel including: Albumin, LDH, AST, ALT, ALP, T.Bili, BUN or serum urea level, creatinine, Ca, Mg, Na, K, Cl, Phosphorus, Glucose, amylase, lipase.
 
TSH and Free T4/Free T3 required within 72 hours of C1D1.
 
Hepatitis B surface antigen (HBV sAg), and hepatitis C antibody (HCV Ab) or Hepatitis C RNA (HCV RNA).
 
Participants who test positive for hepatitis C but test negative for ribonucleic acid are allowed to enroll.

Pregnancy Test (WOCBP Only)	X	Section 9.2.5 . Negative pregnancy test required within 24 hours prior to first dose.
Biomarker Assessments		
Tumor Tissue Sample (Part 1) Archived Tumor Tissue or Recent Tumor Biopsy	X	
Part 1 only: Fresh biopsy required. Archival sample obtained within 3 months of enrollment acceptable for PD-L1 assessment only. See Section 9.6.
 
One (1) formalin-fixed paraffin embedded tumor tissue block or a minimum of 15 unstained tumor tissue sections are acceptable.
 
Specimens must be tested by third party lab to determine PD-L1 status prior to group assignment.

Tumor Tissue Sample (Part 2) Archived Tumor Tissue or Recent Tumor Biopsy		
Part 2 only: Recent sample/fresh biopsy or archival, obtained within 3 months of enrollment.
 
One (1) formalin-fixed paraffin embedded tumor tissue block or a minimum of 15 unstained tumor tissue sections are acceptable. Fresh biopsy tissue is preferred.
 
Specimen collection and shipment to central vendor must be verified prior to treatment assignment. See Section 9.6

EGFR Mutation Status/ ALK Translocation Status (Part 1 and Part 2)	X	Part 1 and Part 2: To be performed by the local lab prior to first dose in all non-squamous participants.

**Table 2-1: Screening Procedural Outline (CA209592) for Part 1 and Part 2**

Procedure	Screening Visit a	Notes
Study Treatment		
Enrollment in IWRS		
	X	Section 7.2. For participant number assignment at the time informed consent is obtained.

a All screening assessments must be completed and participant should be registered for treatment assignment in IWRS within 28 days, unless otherwise noted.

**Table 2-2: On Treatment Procedural Outline (CA209592) for Part 1**

Procedure	On Treatment Visits	Notes 1 Cycle = 6 weeks Visits occur every 2 weeks ( $\pm$ 3 days) to align with nivolumab dose administration.
Safety Assessments		
Physical Examination/Physical Measurements (including performance status)	X	Appendix 5. Weight and ECOG status. Dosing calculations for ipilimumab should be based on the body weight. If the participant's weight on the day of dosing differs by $> 10\%$ from the weight used to calculate the dose, the dose must be recalculated. All doses should be rounded to the nearest milligram. Note: nivolumab dosing is 240 mg flat dosing.
Vital Signs	X	Obtain BP, HR, and temperature just prior to dosing.
Adverse Events Assessment	X	Section 9.2.
Review of Concomitant Medications	X	
Laboratory Tests	X	Section 9.4.1. On-study local laboratory assessments should be done within 72 hours prior to each dose . CBC w/differential, LFTs (ALT, AST, total bilirubin, alkaline phosphatase), BUN or serum urea level, creatinine, Ca, Mg, Na, K, Cl, Phosphorus, LDH, glucose, amylase, lipase.
Thyroid Function Testing	X	TSH + Free T3/T4 required within 72 hours of C1D1, If TSH is abnormal, then TSH with reflexive Free T4, Free T3 is to be performed on Day 1 of each Cycle (every 6 weeks).
Pregnancy Test (WOCBP Only)	X	Serum or urine within 24 hours prior to first dose (C1D1) and then every 4 weeks ( $\pm$ 1 week) regardless of dosing schedule.
Biomarker Assessments		
On Treatment Tumor Biopsy	X See Note.	Section 9.6. To be performed at Cycle 1 Day 29 (Week 5 $\pm$ 1 Week) AND upon documented progression.

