**Table 2-4: Follow-Up and Survival Procedural Outline CA209592 (All Treatment Groups Part 1 and Part 2)**

Procedure	Follow-Up Visits 1 a & 2 b	Survival Follow-up Visits c	Notes
Safety Assessments			
Targeted Physical Examination	X		To assess for potential late emergent study drug related issues.
Vital Signs	X		
Adverse Events Assessment	X		Beyond 100 days from the last dose of study drug, participants will be followed for ongoing drug-related adverse events until resolved, return to baseline or deemed irreversible, or until lost to follow-up, withdrawal of study consent, or start of subsequent therapy.
Laboratory Tests	X		To be done at FU1, to be repeated at FU2, if study related toxicity persists. CBC w/ differential, LFTs, BUN or serum urea level, creatinine, Ca, Mg, Na, K, Cl, Phosphorus, LDH, Glucose, amylase, lipase. If TSH is abnormal, then TSH with reflexive Free T4, Free T3 is to be performed
Pregnancy Test (WOCBP Only)	X		Section 9.2.5.
Efficacy Assessments			
Radiographic Tumor Assessments	X		For participants who discontinue study treatment for reasons other than radiographic PD, follow-up scans should continue to be performed according to the on-study assessment schedule ( Table 2-2 and Table 2-3 ) until PD, withdrawal of consent, or start of subsequent therapy, death, or lost to follow-up After 3 years on study, tumor assessments for long-term survivors can be performed at a frequency per institutional guidelines or every 24 weeks based on NCCN surveillance guidelines.
Collection of Survival Status and Subsequent Therapy Information	X	X	Every 3 months after FU2; May be completed by office visit, phone contact or email, to assess subsequent anti-cancer therapy.

a Follow-up visit 1 (FU1) = 30 days from the last dose +/- 7 days or coincides with the date of discontinuation (+/- 7 days) if date of discontinuation is greater than 35 days after last dose.

b Follow-up visit 2 (FU2) = 100 days (+/- 7 days) from follow-up visit 1

c Every 3 months (+/- 7 days) from FU2

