### **3.3      Benefit/Risk Assessment**

Patients with advanced or metastatic NSCLC represent an important unmet medical need. The clinical activity of nivolumab plus ipilimumab observed to date suggests the potential for improved clinical outcomes in subjects with NSCLC.

Published data from CA209012 study in first line NSCLC, showed confirmed response rates of 39-47% with nivolumab 3 mg/kg Q2w and ipilimumab 1 mg/kg Q6w or Q12w. Activity was observed in both PD-L1 expressing and non-expressing tumors. However, higher response rates were observed in patients whose tumors express PD-L1 ( $\geq 1\%$ ) with a confirmed response rate of 57%).

The safety profile of nivolumab and nivolumab plus ipilimumab is characterized by immune-related toxicities, such as diarrhea, rash, pneumonitis, liver toxicity, and endocrinopathies. The frequencies and intensities of these events in the combination are variable and depend on the specific doses and schedule used. In the dosing schedules selected, these events were mostly low grade, and manageable with the use of corticosteroids.

To assure an ongoing favorable risk/benefit assessment for participants enrolled into CA209592, high-grade, treatment-related adverse events will be closely monitored throughout the conduct of the trial. The Medical Monitor will be responsible for reviewing, on a systematic and continuous

basis, the safety of participants on this study. This includes a review of serious and non-serious adverse events.

More detailed information about the known and expected benefits and risks and reasonably anticipated adverse events (AEs) of nivolumab and ipilimumab may be found in the Investigator's Brochures.

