## **9 STUDY ASSESSMENTS AND PROCEDURES**

Study procedures and timing are summarized in the Schedule of Activities ([Section 2](#)).

- Protocol waivers or exemptions are not allowed.
- All immediate safety concerns must be discussed with the Sponsor immediately upon occurrence or awareness to determine if the participant should continue or discontinue treatment.
- Adherence to the study design requirements, including those specified in the Schedule of Activities, is essential and required for study conduct.
- All screening evaluations must be completed and reviewed to confirm that potential participants meet all eligibility criteria before treatment assignment. The investigator will maintain a screening log to record details of all participants screened and to confirm eligibility or record reasons for screening failure, as applicable.
- Procedures conducted as part of the participant's routine clinical management (e.g., blood count) and obtained before signing of informed consent may be utilized for screening or baseline purposes provided the procedure meets the protocol-defined criteria and has been performed within the timeframe defined in the Schedule of Activities.

Additional measures beyond those described in Section 2, including non-study required laboratory tests, should be performed as clinically indicated or to comply with local regulations. Laboratory toxicities (eg, suspected drug induced liver enzyme evaluations) will be monitored during the follow-up phase via on site/local labs until all study drug related toxicities resolve, return to baseline, or are deemed irreversible.

If a participant shows pulmonary-related signs (hypoxia, fever) or symptoms (eg. dyspnea, cough, fever) consistent with possible pulmonary adverse events, the participant should be immediately evaluated to rule out pulmonary toxicity, according to the suspected pulmonary toxicity management algorithm in the BMS-936558 (nivolumab) Investigator Brochure and [Appendix 7](#).

Some of the assessments referred to in this protocol may not be captured as data in the eCRF. They are intended to be used as safety monitoring by the treating physician. Additional testing or assessments may be performed as clinically necessary or where required by institutional or local regulations.

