#### 9.4.1 Clinical Safety Laboratory Assessments

- Investigators must document their review of each laboratory safety report.
- Screening laboratory assessments should be done locally within 14 days of first dose.
- On-study laboratory assessments should be done locally within 72 hours prior to each dose, as outlined in the Schedule of Activities in Section 2.
- Laboratory assessments should be performed locally at Follow-Up Visit 1, and should be repeated at Follow-Up Visit 2 if study related toxicity persists.

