**Table 9.4.1-1: Laboratory Assessment Panels**

[figure not shown]
Glucose	Magnesium
Albumin (screening only)	TSH, every 6 weeks (Free T3 and T4 performed at screening and reflex to free T3 and T4 if TSH is abnormal at subsequent timepoints) Creatinine clearance (CLcr)- screening only
Urinalysis (As clinically indicated)	
Protein	
Glucose	
Blood	
Leukocyte esterase	
Specific gravity	
pH	
Microscopic examination of the sediment if blood, protein or leukocytes esterase are positive on the dipstick	
Serology	
Serum for hepatitis C antibody or hepatitis C RNA, hepatitis B surface antigen, HIV-1 and -2 antibody (screening only) Testing for HIV must be performed at sites where mandated locally. See Appendix 8 .	
Other Analyses	
Pregnancy test (WOCBP only: as described in Section 2 .)	

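### The on-treatment schedules make the per-cycle TSH conditional on an abnormal TSH, while the laboratory panel requires TSH every 6 weeks for everyone (minor, safety monitoring)

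*Combined protocol and SAP*

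**What the plan says.** **Baseline.** In Table 2-1 the rule is "TSH and Free T4/Free T3 required within 72 hours of C1D1". The thyroid rows of Tables 2-2 (Part 1) and 2-3 (Part 2) open with the same draw.

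**On treatment, Schedule of Activities.** Those two rows then continue, in identical words: "If TSH is abnormal, then TSH with reflexive Free T4, Free T3 is to be performed on Day 1 of each Cycle", followed by a bracketed interval of 6 weeks. The Laboratory Tests row in each table lists its analytes without TSH, although it cites Section 9.4.1.

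**On treatment, laboratory panel.** Table 9.4.1-1 lists "TSH, every 6 weeks (Free T3 and T4 performed at screening", and the same entry adds "reflex to free T3 and T4 if TSH is abnormal at subsequent timepoints".

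**Follow-up.** Table 2-4 has "If TSH is abnormal, then TSH with reflexive Free T4, Free T3 is to be performed" and does not say which TSH is meant.

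**How the texts relate.** Section 9.4.1 describes on-study laboratory work "as outlined in the Schedule of Activities in Section 2". Section 9 adds: "Adherence to the study design requirements, including those specified in the Schedule of Activities, is essential and required for study conduct". Neither ranks the Schedule against the panel.

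**The concern.** Two current tables attach the same condition to different tests. In Tables 2-2 and 2-3 an abnormal TSH is the condition for doing the cycle's TSH. In Table 9.4.1-1 it is the condition only for the follow-on free T3/T4, which presupposes that a TSH was drawn at that visit.

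Taken literally, the schedule rows work backwards. They provide repeat TSH for participants whose TSH is already abnormal, for example some of those whom Section 6.2 admits on thyroid replacement. They provide none for participants with a normal baseline, in whom a new abnormality would be treatment-emergent.

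Thyroid function matters on this regimen. Section 3.3 lists its immune-related toxicities, "such as diarrhea, rash, pneumonitis, liver toxicity, and endocrinopathies". Section 8.1.1 names hyper- and hypothyroidism in its discontinuation rules, and Section 7.4.5.1 has a rule for resuming nivolumab after an endocrinopathy. At stake is uniform detection of asymptomatic thyroid dysfunction across sites, not any efficacy result.

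**Working it through.** The plan gives no figure to reproduce, so the check compares the texts and then counts scheduled tests.

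**Step 1: which test is conditional?**

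| Source | TSH at C1D1 | TSH on Day 1 of later cycles | Free T3/T4 after C1D1 |
|---|---|---|---|
| Tables 2-2 and 2-3, thyroid row | Required | Only if TSH is abnormal | Reflex |
| Table 9.4.1-1 | Required (screening) | Every 6 weeks, no condition | Reflex, if TSH is abnormal |

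**Step 2: does another schedule row fill the gap?** No. Table 2-1 covers the same C1D1 draw, the on-treatment Laboratory Tests rows omit TSH, and Table 2-4 is itself conditional.

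**Step 3: count the scheduled tests for a participant with normal baseline TSH.** Inputs:
- 6-week (42-day) cycles and nivolumab every 14 days (Table 2-2).
- Median exposure of 8 nivolumab and 2 ipilimumab doses in cohort Q of CA209012, the parent cohort on the same schedule (Section 3.2.2).
- Two-year maximum treatment (Section 5.6), taken as 728 days.
- Assumption: dosing on schedule.

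Cycle Day 1 falls on day 1 + 42k, for k = 0, 1, 2, and so on.

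- *Eight nivolumab doses:* days 1, 15, 29, 43, 57, 71, 85 and 99. Cycle Day 1s are days 1, 43 and 85, which leaves 3 − 1 = 2 after C1D1.
- *Two ipilimumab doses:* 2 cycle Day 1s, which leaves 2 − 1 = 1 after C1D1.
- *Two years:* 1 + 42k ≤ 728 gives k = 0 to 17, so 18 cycle Day 1s, the last on day 715. That leaves 18 − 1 = 17 after C1D1.

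| Exposure | Literal thyroid row | Table 9.4.1-1 |
|---|---|---|
| Cohort Q medians | 0 | 1 to 2 |
| Two-year maximum | 0 | 17 |

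**Step 4: time without a scheduled TSH.** With 8 on-schedule nivolumab doses, C1D1 to the last dose is 99 − 1 = 98 days. Under Table 9.4.1-1 the longest gap between draws is 42 days, and the last draw (day 85) precedes the last dose by 99 − 85 = 14 days.

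**The case against.** The strongest reply is that the texts do not truly contradict each other. Nothing says TSH is omitted when baseline is normal; the rows are silent for that participant and Table 9.4.1-1 supplies the rule. Testing every 6 weeks satisfies every text. The thyroid row carries an on-treatment mark and a 6-week interval, and the row above it points to Section 9.4.1. The pointer from that section back to Section 2 may concern only the pre-dose window, and Section 9 does not place the Schedule above the panel. All of this stands as evidence of a misplaced clause and supports a low severity. It does not make the row correct: the sentence still puts the condition on the TSH, and a coordinator working from the visit table could reasonably follow it.

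Other points also stand:
- The row does not say baseline, so a later abnormal TSH drawn for clinical reasons could start per-cycle testing. That still leaves no scheduled test to find the first abnormality.
- Section 8.1.1 mentions thyroid events within an exception that may allow treatment to continue, and neither it nor Section 7.4.5.1 is triggered by a scheduled TSH.
- The two cohort medians do not describe one on-schedule participant, since 8 nivolumab doses span three ipilimumab days. Hence the range of 1 to 2.
- The permitted dosing windows (±3 and ±5 days) can stretch the 42-day gap by some days.
- Harm is limited by adverse event assessment at two-weekly visits, by the provision in Section 9 for clinically indicated tests, and by an endocrinopathy algorithm in Appendix 7, whose flowchart is not shown in the text reviewed.

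**Conclusion.** The concern holds, as a minor point confined to safety monitoring. The thyroid rows of Tables 2-2 and 2-3 are wrong as written against Table 9.4.1-1, most likely through a drafting slip.

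The counts above describe the literal reading with on-schedule dosing, at a site that overlooks Table 9.4.1-1. They are not an expected effect, because the documents give no basis for how many sites would read the row that way. Objective response rate, the TMB analyses and the sample size are untouched.

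**What to change.** In Tables 2-2 and 2-3, replace the thyroid wording with: *TSH + free T3/T4 within 72 hours of C1D1, then TSH on Day 1 of every cycle (every 6 weeks) for all participants, with reflex free T3/T4 if TSH is abnormal.* Leave Table 9.4.1-1 as it is.

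In Table 2-4, say which TSH the clause refers to, for example the last on-treatment one. A TSH for everyone at FU1 would be an optional addition, not a correction.

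As separate housekeeping, the 19-day minimum in the Dispense Study Treatment rows has no support elsewhere. It could be replaced by the minimums stated in Sections 7.1.1 and 7.4.5.2: 12 days between nivolumab doses, and 6 weeks (less the 5-day window) between ipilimumab doses. No effect on dosing is claimed.

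**Cost:** a text correction in the next amendment or an administrative letter. The on-treatment wording adds no test beyond Table 9.4.1-1, and the Table 2-4 clarification adds none. The optional FU1 TSH would be one new test per participant on a draw already planned.
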